***1. Purpose/Specific Aims***

This study will modify our existing 8-session, individual counseling treatment manual (“Persistence Targeted Smoking Cessation (PTSC)”) to make it more feasible for treating smokers with schizophrenia. We will also test the ability of our new treatment, “Persistence Targeted Smoking Cessation in Schizophrenia (PTSC-S)” to increase task persistence in smokers with schizophrenia.

***1.1 Objectives***

We will demonstrate that our new treatment “Persistence Targeted Smoking Cessation in Schizophrenia (PTSC-S)” is feasible for treating smokers with schizophrenia and that it increases their task persistence.

***1.2 Hypotheses***

1. We hypothesize that at least 80% of participants will rate the intervention as “easy to understand” and “helpful” on a post-intervention exit interview questionnaire.
2. We hypothesize that smokers with schizophrenia receiving our PTSC-S intervention will demonstrate cognitive and behavioral increases in task persistence from baseline to follow-up.

***2. Background and Significance***

We propose to modify a theory-based smoking cessation intervention (called Persistence-targeted smoking cessation; PTSC) to make it more feasible for treating smokers with schizophrenia. We will include 8 weekly individual counseling sessions and use of the nicotine patch for 10 weeks. We will provide counseling sessions and nicotine patches free of charge to research participants. We will test the feasibility of the intervention and its ability to influence persistence (measured as described in the table in section 4.2). We hope to develop a feasible psychosocial treatment for use in a later randomized controlled trial.

***Summary of Proposed Project in Lay Terms and Scientific Terms:***

This study is a non-randomized trial of a new psychosocial treatment for smoking cessation (for smokers with schizophrenia) that is based on cognitive behavioral therapy for smoking cessation – a commonly used approach. Participants will receive free weekly counseling (8-weeks) and free nicotine patches (10-weeks). They will complete assessment measures

commonly used in smoking cessation studies. We hope to show that this treatment is feasible in this small pilot study before comparing it to a more established treatment in a future RCT.

### **3. Research Design and Methods**

We will conduct an open trial (N=26) of our 8-session, weekly, individual treatment, (Persistence Targeted Smoking Cessation for Schizophrenia (PTSC-S)). The purpose of this open trial will be to “begin to demonstrate that the intervention alters the targeted mechanism (thus providing an initial proof of principle).” We will measure task persistence via behavioral and cognitive measures administered in counterbalanced order at baseline, after session 3, and at one- and three-months post-quit date. By assessing task persistence at multiple follow-up points, we will be able to examine how many sessions are required to produce an effect (i.e., effect of treatment “dose”).

A trained research assistant (who will receive weekly and as-needed supervision from the principal investigator) will pre-screen potential participants on the phone, followed by obtaining informed consent and administering the baseline assessment battery (see Assessment Measures table below). We will divide the baseline assessment battery into two sessions to minimize participant fatigue. Each baseline assessment session will last approximately 90 minutes. We will then provide free, weekly individual counseling sessions for 8 weeks and 10-weeks’ worth of the nicotine transdermal patch (an FDA-approved smoking cessation product available over the counter). All sessions will be audio recorded for treatment integrity and supervision.

Questionnaires that are commonly used in tobacco dependence treatment studies will be used in the current study. Women of childbearing age will take a pregnancy test to rule out pregnancy. Carbon monoxide (CO) levels (also commonly collected in tobacco dependence treatment studies) will be assessed with a carbon monoxide monitor and CO reading in parts per million (ppm) will be recorded. The carbon monoxide monitor used will be the *Bedfont Scientific Ltd. Micro+ Smokerlyzer*. The Micro+ Smokerlyzer is a hand-held, battery powered instrument which uses electrochemical technology to sample the gas and a microprocessor to convert the output from the sensor to a carbon monoxide (CO) concentration. The result and menus are displayed on a color LCD and an accompanying buzzer sounds in response to the CO level. The instrument is controlled using a touch screen operation and has a USB link to a computer to download readings.

The Micro+ uses a breath sampling D-Piece with integrated bacterial and viral filter and a one-way valve designed to maximize infection control. Each patient uses a fresh mouthpiece for each breath sample. The D-Piece may be reused or replaced as required.

The patient is asked to hold their breath for a 15 second countdown. This is displayed on the screen of the device. At the end of the breath hold, the patient blows gently into the Micro+ expiring as much of the breath in their lungs as possible. The reading on the device shall rise until the peak reading is held on the display.

A research assistant will provide instructions on how to use the CO monitor and will record the results at baseline and followup appointments. A research therapist will do so during the 8 counseling sessions. The study PI is accountable for the device.

#### **3.1. Duration of Study**

Participants will be active in the study for approximately 4 months. We anticipate completing data collection activities within 24 months.

### **3.2 Study Sites**

Participants will be daily smokers primarily from central New Jersey. Participants will attend treatment at our Addiction Psychiatry office at [name]. We will also recruit participants from several University Behavioral Health Care (UBHC) locations, including: New Brunswick, Piscataway, Monmouth Junction, and Edison. If it proves more convenient for participants to receive counseling at UBHC locations, we will provide services in those locations instead of at our [name] office.

### **3.3 Sample Size Justification**

26 participants will be enrolled.

We will enroll 26 smokers from the local area. We will collect demographic data that will allow us to compare this sample to the general population of smokers. This is a non-randomized, pilot, feasibility study so a power analysis is not applicable to this study design.

### **3.4 Subject Selection**

#### **3.4.1 Inclusion Criteria**

- Must be between 18 – 64 years old
- Must indicate commitment to quitting smoking in the next 30 days
- Must smoke at least 5 cigarettes (including those labeled “little cigars”) per day for past 6-months
- Expired breath carbon monoxide (CO) > 5 to ensure daily cigarette use
- Must score < 8 (or <7 for women) on the Alcohol Use Disorders Identification Test
- Must score less than 3 on the 6-month Drug Abuse Screening Test-10
- Must provide a negative urine drug screen for cannabis, cocaine, or opiates (Note: Participants with a positive screen for opiates may participate with proof of prescription for opiates.)
- Must have a diagnosis of Schizophrenia or Schizoaffective Disorder on SCID-I
- Psychiatric illness must be stable, as indicated by no hospitalizations in previous 8 weeks, and a stable psychotropic medication regimen including a stable antipsychotic dose for 8 weeks
- Must have a working phone (for feasibility of follow-up and for ability to receive optional SMS text messages)

#### **3.4.2 Exclusion Criteria**

- Must not be currently receiving tobacco dependence treatment counseling
- Must not currently be taking varenicline (Chantix),
- Must not be taking bupropion (Zyban/Wellbutrin) to quit smoking
- Must not be taking any nicotine preparations (gum, lozenge, patch, spray, inhaler) daily over the last 10 days
- Must not report myocardial infarction in the past year, unstable angina pectoris, , or significant cardiac arrhythmia (including atrial fibrillation) in the past 90 days.
- Must not be pregnant, breastfeeding, or planning on becoming pregnant in the next 4-months. Women who can become pregnant may be included if using effective birth control

- Must not have pending legal matters with potential to result in jail time
- Must not be planning on moving outside local area in next 3-months

Participants answering “yes” to any item on the “Nicotine Patch Contraindications Form” will meet with an Addiction Psychiatrist for follow-up and approval for the study. The Addiction Psychiatrist will document this assessment in signed progress notes.

***Justification of exclusion of any sub-segment of the population:*** Children will not be included in the study because young children are unlikely to be daily smokers and the nicotine patch (which will be used in this study) is not currently FDA approved for children. All participants must be at least 18 years old to participate in this study.

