### ***5.2 Subject Costs and Compensation***

Participants will be paid \$100 through the duration of the study. They will receive \$40 at the baseline assessment (\$10 for first baseline session, \$30 for second baseline session), \$10 at the Quit Date assessment, \$30 at session 8, and \$20 at the 3-months post-quit date assessment.

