## **6. Data Handling**

As this study is primarily a feasibility study, our data analysis plan will primarily comprise descriptive statistics such as mean (sd) sessions attended and percent of participants reporting 3-months post quit-date abstinence. We need to collect all of this data in order to demonstrate that our PTSC treatment manual is generalizable to a population of smokers with schizophrenia. We need to examine changes in relevant variables such as self-reported cigarette and medication use, withdrawal, smoking urges, and mechanisms of change in order to evaluate the efficacy of our treatment.

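### The relocation exclusion looks 3 months ahead, but the final assessment falls about 4 months after screening, so its in-person measures are not fully protected (minor)

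*Combined protocol and SAP*

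**What the plan says.** The relocation criterion in Section 3.4.2 reads "Must not be planning on moving outside local area in next 3-months". The same list uses a longer horizon for pregnancy plans: "planning on becoming pregnant in the next 4-months". Section 3.1 states: "Participants will be active in the study for approximately 4 months".

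The last contact is timed from the Quit Date and not from enrolment. Section 3 places the persistence assessments "at baseline, after session 3, and at one- and three-months post-quit date", the table in Section 4.2 has a final column at 3 months post Quit Date, and Section 5.2 (Subject Costs and Compensation) lists the last payment, in dollars, as "20 at the 3-months post-quit date assessment".

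Several steps come before the Quit Date: a telephone pre-screen, consent, a baseline split in two ("We will divide the baseline assessment battery into two sessions to minimize participant fatigue") and early counselling. No section gives the calendar week of the Quit Date. Section 3.4.1 requires only this: "Must indicate commitment to quitting smoking in the next 30 days".

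No other eligibility criterion covers a planned move in the fourth month. The nearest is the working-phone requirement in Section 3.4.1.

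**The concern.** A look-ahead of 3 months from screening cannot reach a visit set 3 months after a later date. The part of follow-up left uncovered is the part that contains the final assessment. A person who says at screening that they will leave the area in month 4 meets this criterion as written.

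The table in Section 4.2 schedules expired CO, mirror tracing, breath-holding and the sustained divided attention task at that visit, along with questionnaires and the smoking timeline. Section 6 also names "percent of participants reporting 3-months post quit-date abstinence" as a descriptive outcome. A loss from a move already planned at screening is foreseeable, unlike ordinary dropout, and a 26-person pilot meant to prepare for a randomized trial has little data to spare.

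**Working it through.** **Inputs from the protocol.** Relocation look-ahead: 3 months (Section 3.4.2). Participation: about 4 months (Section 3.1). Final visit: Quit Date + 3 months (Sections 3, 4.2 and 5.2). Eight weekly sessions (Section 3). Quit commitment: within 30 days (Section 3.4.1).

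**Assumptions, not in the documents.** Let b be the weeks from screening to session 1, taken as 0 to 2. Let q be the weeks from session 1 to the Quit Date, taken as 2 to 4. The range for q is suggested by the assessment after session 3 in Section 3 and by the withdrawal scale being given before sessions 4 through 8 (footnote to the Section 4.2 table). One month is 30.44 days, so 3 months is 91.3 days and 4 months is 121.75 days.

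**Step 1: reproduce the stated duration.** With b = 1 and q = 3, the final visit is at 7 × (1 + 3) + 91.3 = 119.3 days, or 3.92 months. As a cross-check, quitting at the end of the 30-day window gives 30 + 91.3 = 121.3 days, or 3.99 months. Both agree with Section 3.1.

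**Step 2: compare the window with the final visit.** Final visit day = 7(b + q) + 91.3. The window ends at day 91.3. Shortfall = 7(b + q) days.

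| Case | b | q | Final visit (day) | Months | Shortfall (days) |
|---|---|---|---|---|---|
| Fastest | 0 | 2 | 105.3 | 3.46 | 14 |
| Central | 1 | 3 | 119.3 | 3.92 | 28 |
| Slowest | 2 | 4 | 133.3 | 4.38 | 42 |

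The shortfall is zero only if b + q = 0, that is, if the Quit Date is the day of screening. The design does not work that way, so the direction of the result does not depend on the assumed values; only its size does.

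**Step 3: locate the tested endpoint.** With weekly sessions and none postponed, session 8 falls at day 7(b + 7), which is day 49, 56 or 63 for b = 0, 1 or 2 (1.6 to 2.1 months). All three lie inside the 91-day window.

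**Step 4: test a 4-month look-ahead.** It ends at day 121.75. That covers the fastest and central cases and leaves 133.3 − 121.75 = 11.6 days, about 12, in the slowest. Wording tied to the visit itself leaves no gap.

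**The case against.** The strongest reply is that little of the planned analysis is exposed, and most of that reply stands.

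- **Main analyses.** In the Section 4.2 table the exit interview for hypothesis 1 is scheduled no later than session 8. The paired t-tests and linear contrasts for hypothesis 2 (Section 7) run from baseline to session 8. Only the mixed model might use the 3-month point, and it can retain participants who miss that visit. A reader might infer that the mismatch undermines the hypothesis tests; it does not.
- **Fallback visits.** A reader might infer that anyone who moves can give only a telephone interview. The data collection text in Section 6 first offers a meeting in a public place that suits the participant, with telephone as the last resort. The CO monitor is hand-held, and the protocol does not define the local area. A short move need not prevent an in-person visit.
- **Abstinence.** It is tempting to say that each mover costs 1/26 = 3.8 percentage points of the abstinence rate. That needs a participant who cannot be reached at all and a rule counting missing as smoking. Section 6 words the outcome as self-report, which a telephone call can supply, and the plan states no such rule.
- **Purpose.** The protocol gives no reason for the relocation criterion. It may have been meant to secure attendance at counselling, which 3 months covers. The 4-month pregnancy criterion shows the horizon used elsewhere in the list; it does not prove that the 3-month figure is a slip.
- **Trade-off.** The people a longer window would exclude could finish counselling and supply the session-8 data.

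What the reply does not remove is the data a telephone call cannot supply. It gives no CO reading, and the plan describes no remote form of mirror tracing, breath-holding or the attention task. For a participant who has moved out of practical reach, those 3-month measures are lost.

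**Conclusion.** The mismatch is real and minor. The relocation window ends before the final assessment under any schedule in which the Quit Date follows screening. The gap is about 14 to 42 days, centrally 28, under the assumed baseline and Quit Date timings. A firm minimum of 3 weeks would be too strong, because it needs a Quit Date at session 4, which the documents do not state.

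The exposure is confined to the 3-month expired CO, mirror tracing, breath-holding and attention task, in people who already plan a move beyond in-person reach. The documents give no rate of planned moves, so the expected number cannot be calculated; it is probably very few of the 26.

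**What to change.** Reword the relocation criterion in Section 3.4.2 to exclude anyone who plans to leave the local area before the 3-month post-quit-date assessment, and add in brackets that this is about 4 months from screening. This agrees with Section 3.1 and is safer than changing 3 to 4, since a fixed 4 months could still fall about 12 days short in the slowest case. Make the same change on any screening form that carries the criterion.

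The cost is one line of text and a very small number of extra exclusions, among people who could have completed counselling and the session-8 measures. If the investigators prefer to keep those people, they can leave the criterion as it is and say that some 3-month in-person measures may be missing because of planned moves.

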#### **4. Study Variables**

##### ***4.1 Independent Variables or Interventions***

We will provide 8-weeks of free counseling to participants. Study therapists will utilize the “Persistence-Targeted Smoking Cessation-Schizophrenia (PTSC-S)” manual developed by [name], which is based on cognitive behavioral therapy. PTSC-S is an 8-session, individual, smoking cessation counseling strategy that focuses heavily on using cognitive behavioral therapy targeted at disputing automatic thoughts that may reduce task persistence for smokers with schizophrenia. While disputing automatic thoughts will be the focus of each session, skill building and support will also be included. Participants will be asked to complete homework assignments between sessions – including keeping a daily thought record to monitor automatic thoughts that may put them at risk for smoking. A daily thought record is a commonly used cognitive behavioral therapy homework assignment in which participants practice identifying and evaluating their thoughts. Participants will also track their daily cigarette use and nicotine patch use for homework. Participants will use commonly used, established measures to provide brief assessment information at the end of each session (i.e., nicotine dependence, tobacco use, nicotine lozenge use, nicotine craving, and nicotine withdrawal).

###### ***4.1.1 Drug or Device Interventions***

We will give participants a 10-week supply of the nicotine transdermal patch (an FDA-approved, over-the-counter medication) to be used starting on their Quit Date. Although the nicotine patch is commercially available without a doctor’s prescription, Co-I [name] (an addiction psychiatrist) will provide medical monitoring during this study. Consistent with the product insert, participants will be instructed to use one nicotine patch daily, and to apply it upon awakening at about the same time each day. Subjects will be instructed to vary the site of application of the patch daily to minimize any skin irritation. They will use the 21mg patch for the first 8-weeks, then 2-weeks of the 14mg patch.

#### 4.2 Dependent Variables or Outcome Measures

Assessment measures: See table below

Concept	Measure	B/L	Weekly	QD	Session 8	3-mo. Post QD
DEMOGRAPHICS	Smoking History & Demographics Questionnaire (includes National Health and Nutrition Examination Survey (NHANES) items)	X				
TOBACCO USE	Fagerström Test for Nicotine Dependence (Heatherton et al., 1991)	X				
	Timeline Followback (TLFB; Sobell & Sobell, 2000)		X	X	X	X
	Current Tobacco Use – \$ spent, menthol use, night-time smoking	X				
	Expired Breath Carbon Monoxide (CO)	X	X	X	X	X
	Brief WISDM	X				
NRT USE	Self-reported use of patch – including visual inspection of patch		X	X	X	X
	NRT side effects		X	X	X	X
	Nicotine patch contraindications form	X				
CRAVING AND WITHDRAWAL	Wisconsin Smoking Withdrawal Scale (Welsch et al., 1999)	X	X*	X	X	
MOTIVATION TO QUIT SMOKING	ICT – Change Measure (includes self-efficacy) (Miller & Johnson, 2008)	X		X	X	
	Quitting Fatigue			X	X	X
	Commitment to Quitting Smoking Scale (CQSS)	X		X	X	
ANHEDONIA	Temporal Experience of Pleasure Scale (Gard et al., 2006)	X		X	X	X
	Snaith - Hamilton Pleasure Scale (Snaith et al., 1995)	X		X	X	X
	Tripartite Pleasure Inventory (Leventhal, 2010)	X		X	X	X
TASK PERSISTENCE	Mirror Tracing	X		X	X	X
	Breath-holding	X		X	X	X
	Temperament and Character Inventory—Persistence Scale (TCI-P)	X		X	X	X
	2-item Task Persistence Measure	X		X	X	X
	Distress Tolerance Scale (DTS)	X		X	X	X
	Sustained Divided Attention Task	X		X	X	X
	Thoughts About Smoking Questionnaire	X		X	X	X
	Daily Habits Questionnaire	X				
SUBSTANCE USE / MENTAL HEALTH ISSUES	Alcohol Use Disorders Identification Test (AUDIT; Babor et al., 2001)	X				
	6-month Drug Abuse Screening Test – 10 (DAST-10; Skinner, 1982)	X				
	Urine drug screen (for cannabis, cocaine, opiates)	X				
	SCID-RV for DSM 5 - Modules A, B, and C	X				
	Brief Symptom Inventory (BSI; (Derogatis, 1975)	X				
	CES-D	X	X	X	X	X
INTERVENTION INTEGRITY / FEASIBILITY	Exit interview		X	X	X	
	Study created integrity measure		We will confirm treatment integrity throughout the study			

\*Wisconsin Smoking Withdrawal Scale will be administered before sessions 4 through 8

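### The early task-persistence battery is placed after session 3 in Section 3 but at the Quit Date in Table 4.2, and under the table no post-baseline score is scheduled before the day the patch and quit attempt begin

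*Combined protocol and SAP*

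**What the plan says.** The documents give two schedules for the persistence measures.

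- **Section 3 (Research Design and Methods):** the measures are "administered in counterbalanced order at baseline, after session 3, and at one- and three-months post-quit date". The same paragraph says that repeated follow-up will let the team work out how many sessions it takes to see an effect, that is, the dose of treatment.
- **Section 4.2 (assessment table):** the persistence tasks and scales, including the row "Sustained Divided Attention Task", are ticked at baseline, QD, session 8 and 3 months after the Quit Date. Their Weekly cells are empty.
- **Section 5.2 (Subject Costs and Compensation):** $10 is paid "at the Quit Date assessment", so the Quit Date is a real assessment visit.
- **Section 4.1.1:** the patch is "to be used starting on their Quit Date", and participants are told "to apply it upon awakening at about the same time each day".

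No section ties the Quit Date to a session. The nearest clue is the table footnote, which starts the weekly withdrawal ratings at session 4. This suggests a Quit Date around session 3 or 4 but does not state it.

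Section 7 tests hypothesis 2 with paired t-tests and linear contrasts from baseline to session 8. Any other time point enters only through time in the mixed model.

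**The concern.** The trial has one arm. Before the Quit Date, participants have had some counseling but no study patch and no planned quit attempt. A persistence score taken then would be free of both influences. The Section 3 schedule may contain such a score; the table does not.

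On the table's schedule, a change from baseline to the first follow-up coincides with the start of nicotine replacement and of quitting. Breath-holding, sustained attention and self-reports about smoking could plausibly move with nicotine state, in either direction. A rise could then be credited to a few counseling sessions when it came from the patch, or a real gain could be masked by withdrawal. What is at stake is the Section 3 question about the number of sessions, and with it the claim that the counseling acts on its intended mechanism.

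**Working it through.** The plan gives no power, alpha or effect-size figure to reproduce; Section 3.3 sets n=26 and says that a power analysis does not apply. The check is therefore a calendar, followed by an illustration.

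**1. Calendar.** Inputs from the documents: 8 weekly sessions, patch for 10 weeks (70 days) from the Quit Date, of which the first 8 weeks (56 days) are at 21 mg. Assumptions: session k falls on day 7(k−1), and 3 months is 91 days. Because the Quit Date is not anchored, four positions were tried.

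| Assumed Quit Date | Day | Session 8 (day 49) after Quit Date | End of session 3 (day 14) before Quit Date |
|---|---|---|---|
| Day of session 3 | 14 | 35 days (5.0 weeks) | 0 days |
| Day after session 3 | 15 | 34 days (4.9 weeks) | 1 day |
| Session 4 | 21 | 28 days (4.0 weeks) | 7 days |
| Session 5 | 28 | 21 days (3.0 weeks) | 14 days |

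- Quit Date battery: same day as the scheduled patch start.
- Session 8 battery: 21 to 35 days after the Quit Date, below 56 in every case, so within the 21 mg period.
- 3-month battery: 91 − 70 = 21 days after the patch supply ends, so off patch if used as scheduled, but after patch exposure and the quit attempt.

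Under the table, 0 of 3 post-baseline batteries come before the day the patch and quit attempt begin. Under Section 3, a battery at the end of session 3 would come before that day in 3 of the 4 assumed cases.

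**2. Illustration of size.** This is a two-sided 0.05 paired comparison of baseline with the early battery, which Section 7 does not plan. Suppose that counseling has no effect and that nicotine state shifts scores by s (in SD units). With within-person correlation r:

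- SD of change = √(2(1−r))
- standardized change d = s / √(2(1−r))
- noncentrality = d√26, with 25 degrees of freedom and critical t = 2.06

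| r | SD of change | d at s=0.2 / 0.3 | Chance of a significant increase |
|---|---|---|---|
| 0.4 | 1.095 | 0.183 / 0.274 | 14% / 27% |
| 0.6 | 0.894 | 0.224 / 0.335 | 19% / 38% |
| 0.8 | 0.632 | 0.316 / 0.474 | 34% / 64% |

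With s=0 the chance is 2.5%. The documents give neither s nor r.

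**The case against.** **The order of events on the Quit Date is not stated.** A reader might infer that the battery is taken in the first hours on the patch and without cigarettes, by joining the instruction to "apply it upon awakening at about the same time each day" to the QD tick. The table also ticks patch use, "including visual inspection of patch", at that visit. This is plausible, but no section gives the hour of the battery, its order relative to the first patch, or whether smoking has stopped. Only the shared day is supported. For the same reason, it cannot be said that exactly three sessions precede the Quit Date.

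**Section 3 may already contain the wanted score.** This stands. It is why the firm finding is a conflict between sections, not a settled flaw in timing.

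**Moving the battery would not isolate counseling.** This stands too. A reader might take a pre-quit change as the effect of counseling alone. With no control arm, it still mixes counseling with practice on the tasks, regression to the mean, elapsed time and any pre-quit change in smoking. The move removes the patch and quitting components only.

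**The combined treatment is a legitimate target.** Section 2 describes counseling plus patch, and the tested contrast is baseline to session 8. For that contrast the point affects only how the result is described. But Section 4.1 defines PTSC-S as a counseling approach, and Section 3 asks its dose question in sessions. A package effect cannot answer that question.

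**The percentages attach to no planned test.** Correct. They are illustrative only.

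**Conclusion.** The concern holds in this form: Section 3 conflicts with the Section 4.2 table and the payment schedule on when the early battery is given, and the Quit Date is not anchored to a session. Under the table, none of the three post-baseline batteries is scheduled before the day the patch and quit attempt begin. The early change then cannot separate counseling sessions from nicotine replacement and quitting, and this weakens the aim of examining how many sessions are needed.

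The calendar result for the table does not depend on where the Quit Date falls among the four positions tried. The 14% to 64% range depends wholly on an assumed shift of 0.2 to 0.3 SD and an assumed correlation of 0.4 to 0.8. It concerns an unplanned comparison, and the true shift could be zero. The documents do not support saying that the planned hypothesis 2 test has such an error rate. The change is worth making because it is cheap and serves a stated aim.

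**What to change.** 1. **Schedule.** Reconcile Section 3, the Section 4.2 table and the payment text. Move the task-persistence rows of the QD column to the existing session 3 visit, completed before the Quit Date and first patch. Leave CO, withdrawal and patch items at the Quit Date. The Quit Date and the patch schedule do not change. In the same edit, resolve the other mismatch: Section 3 lists one month post-quit where the table has session 8.
2. **Anchor.** State which session the Quit Date follows. If it is the day of session 3 itself, the plan must say how the battery is completed beforehand, or not call the score pre-quit.
3. **Data.** Add time since last cigarette at each battery. Patch use, CO and Timeline Followback are already collected at the Quit Date, session 8 and 3 months.
4. **Section 7.** Add the baseline-to-session-3 change as an uncontrolled pre-patch, pre-quit change. Describe the baseline-to-session-8 change as the uncontrolled effect of counseling plus patch plus quitting.

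**Cost.** A protocol amendment, a longer session 3 visit, one added question per battery and a small change to the payment wording. The tasks and the number of batteries stay the same.
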